6.2 Study Dates

Informed Consent Date

The date on which subject signs the informed consent form.

eDiary Device Assignment Date

The date on which an eDiary device is assigned to a subject for the first time after completion of initial screening at week -4 visit.

Randomization (Enrollment) Date in DBTP

Randomization (Enrollment) Date in DBTP is the date on which a subject is assigned to one of the treatments through Interactive Voice Response System (IVRS) in DBTP.

First IP Dose Date

First IP Dose Date is the date on which a subject is administered the first dose of investigational product following randomization, which may be the same day or after the randomization date. For subjects who are randomized but not dosed with double-blind IP after randomization, First IP Dose Date is considered missing.

First OLTP IP Dose Date

First OLTP IP Dose Date is the date on which a subject is administered the first dose of investigational product in the open-label treatment phase following completion of DBTP.

Last IP Dose Date

Last IP Dose Date for each subject is defined as the latest date IP is administered.

End of IP Admin Date

End of IP Admin for each subject is defined as the date the decision was made to end IP as recorded on the End of IP eCRF page.

Subject-level End of Study (EOS) Date

End of study (EOS) date for each subject is defined as the last date on which the subject participated in the study. The date will be recorded on the End of Study eCRF page.

Primary Completion Date

The Primary Completion Date is the date of the End of Double-Blind Treatment Phase page for the last subject who completes DBTP.

Study Completion Date

The Study Completion Date is the EOS date of the last subject in the study.

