6.3 Study Points of Reference

Baseline Assessment

Baseline assessment is defined as the last non-missing measurement for the endpoint of interest taken before the first dose of investigational product. In cases where baseline measurements are taken on the same day as IP, it will be assumed that these measurements are taken prior to IP being administered. For subjects who are randomized but not dosed after the randomization, the baseline of the study is defined as the last non-missing measurement prior to or on the date of randomization.

For C-SSRS, if subject completes C-SSRS form on Day 1 then all individual items from Day 1 visit will be used as baseline. If subject does not complete C-SSRS form on Day 1 then all individual items from Week -4 visit will be used as baseline.

Baseline assessment of data collected from eDiary will be summarized as monthly measurements using data collected during baseline period. See [Section 6.1.1](#) for detail.

Study Day 1

Study Day 1 is defined as the first IP dose date. For subjects who are randomized but not dosed after randomization, the Study Day 1 is defined as the date of randomization.

Study Day

Study Day is defined as the number of days from Study Day 1.

Before Study Day 1:

Study Day = (Date of Interest – Date of Study Day 1)

On or after Study Day 1:

Study Day = (Date of Interest – Date of Study Day 1) + 1

Therefore the day prior to Study Day 1 is -1.

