10.1 General Principles

The primary objective of this study is to evaluate the effect of AMG 334 compared to placebo on the change from baseline in mean monthly migraine days, in subjects with episodic migraine.

The primary analysis will be performed when the last randomized subject completes the week 24 assessment or is discontinued from the study. The final analysis for the study including DBTP, OLTP and safety follow-up phase will be performed at the end of the study.

Subjects will be analyzed based on their randomized treatment group assignment.

Summary descriptive statistics by each treatment group will be tabulated at each visit. For continuous endpoints, the descriptive statistics include: number of observations, mean, median, standard deviation, first and third quartiles, minimum and maximum. For categorical and ordinal endpoints, frequency and percentage will be given.

Change from baseline for efficacy endpoints will be summarized using both the study baseline and the pre-OLTP baseline for efficacy endpoint, respectively.

Primary analyses for efficacy endpoints are based on a linear mixed effects model including appropriate terms and covariates in the model (See [Section 4.2](#)). Nominal p-values will be provided for the comparisons between each AMG 334 treatment group vs. the placebo group for efficacy endpoints. To maintain a family-wise type I error at 0.05, the pair-wise comparison will be tested in a sequential testing procedure in the order of AMG 334 140 mg vs. placebo, 70 mg vs. placebo and 28 mg vs. placebo. The lower dose group will be tested only when the higher dose group is considered statistically significant. For continuous efficacy endpoints, the adjusted mean change from baseline

for each treatment group, and the adjusted treatment difference compared to placebo, associated 95% confidence intervals, and p-values for pairwise comparison will be reported. For dichotomous efficacy endpoints, adjusted odds ratios compared to placebo, associated 95% confidence intervals, and p-values will be reported. Randomized stratum (stratification group) will be included in the statistical models for the efficacy endpoints. However, the actual data collected will be used for the analysis of baseline characteristics and subgroup analyses.

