10.6.2 Laboratory Test Results

Shifts tables of the laboratory toxicity for absolute neutrophil count (ANC) based on CTCAE grade relative to baseline will be tabulated by treatment group for each study phase.

Summary of change from baseline for ANC, alanine transaminase (ALT) and aspartate aminotransferase (AST) will also be provided by visit for each study phase.

Subject incidence of liver function test abnormalities (including AST, ALT, Total Bilirubin (TBL) and Alkaline Phosphatase (ALP)) will also be summarized by treatment group and study phase.

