10.6.4 Columbia-Suicide Severity Rating Scale (C-SSRS)

No statistical testing will be performed on C-SSRS. The number and percentage of subjects reporting any suicidal ideation and any suicidal behavior will be summarized descriptively by treatment group separately for the DBTP and OLTP. Shift table of C-SSRS maximum severity of suicidal ideation/behavior compared to baseline will be provided by treatment group separately for the DBTP and OLTP.

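### Open-label ANC shifts and ANC, ALT and AST changes are measured from the pre-double-blind baseline, so in placebo-randomised subjects an abnormality that arose on placebo and persists is tabulated in both phases

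*SAP*

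**What the plan says.** **Baseline.** SAP 6.3 states: "Baseline assessment is defined as the last non-missing measurement for the endpoint of interest taken before the first dose of investigational product". SAP 6.2 fixes what the first dose means: "First IP Dose Date is the date on which a subject is administered the first dose of investigational product following randomization". For the placebo arm that dose is placebo. SAP 6.2 also defines a separate anchor, "First OLTP IP Dose Date is the date on which a subject is administered the first dose" in the open-label phase, but the laboratory baseline does not use it.

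**Laboratory tables.** SAP 10.6.2 says the ANC shift tables are "based on CTCAE grade relative to baseline will be tabulated by treatment group for each study phase". The change summaries for ANC, ALT and AST "will also be provided by visit for each study phase". No other baseline is named. Protocol 10.5.5 also refers only to baseline and analyses the two phases separately.

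**Efficacy.** SAP 10.1 treats efficacy differently: "Change from baseline for efficacy endpoints will be summarized using both the study baseline and the pre-OLTP baseline for efficacy endpoint, respectively". Safety endpoints have no counterpart.

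**Treatment and grouping.** All subjects who enter the open-label phase receive AMG 334 (SAP 3.1.2; Protocol 6.2.1.1). SAP 10.6 groups safety tables by randomised treatment. Protocol 10.4.4 also plans open-label tables pooled over all AMG 334 subjects.

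**The concern.** In the open-label phase every value is taken on AMG 334, so a shift in that phase will be read as something seen on the drug. For placebo-randomised subjects the reference precedes 24 weeks without drug, and anything that changed in those weeks and lasted is carried into the open-label column. The same abnormality is then reported twice, once correctly under placebo and once in a phase that contains only active treatment.

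These subjects are also the only ones who begin AMG 334 after a long observed drug-free period. Their change from just before the first open-label dose is the cleanest within-subject view of first exposure, and no planned laboratory table shows it. Long-term safety is a stated objective (SAP 2.3).

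**Working it through.** The plan states no figure on this point, so there is none to reproduce. The check has four parts.

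**1. Which samples exist.** Protocol Table 2 schedules hematology and chemistry on Day 1 and at Weeks 4, 12 and 24. Table 3 schedules them at Weeks 28, 36, 52, 76 and 100. The SAP covers the protocol version whose open-label phase ends at Week 76, which gives four open-label draws. The current protocol gives five. A pre-open-label value is normally available at Week 24.

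**2. The rule applied to example grades in a placebo-randomised subject** (worst grade per phase; Week 24 sample taken before the open-label dose and counted as double-blind):

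| Course | Double-blind shift | Open-label, study baseline | Open-label, pre-open-label baseline |
|---|---|---|---|
| Grade 2 at Weeks 12, 24, 28, 36 | 0 to 2 | 0 to 2 | 2 to 2 |
| Grade 2 at Weeks 4 and 12, resolved by Week 24 | 0 to 2 | 0 to 0 | 0 to 0 |
| New grade 2 at Week 28 | 0 to 0 | 0 to 2 | 0 to 2 |

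Only the persistent abnormality is counted twice. A true new open-label event appears under either baseline.

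**3. The phase boundary.** The safety windows in SAP 6.4 end the double-blind phase on the first open-label dose date and start the open-label phase on that same date. Protocol 7 requires all procedures of a visit on one day, and Protocol 7.2.24 gives the first open-label dose after the Week 24 procedures. A pre-dose Week 24 sample therefore falls in both windows. A subject with grade 2 at Week 24 only would show an open-label shift of 0 to 2 if that sample is included, and 0 to 0 if it is not. The study-visit table in SAP 6.4 adds to this. For subjects dosed at Week 24, it closes the Week 24 window the day before the dose and opens the Week 28 window on the dose date.

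**4. Size.** The documents give no laboratory abnormality rates, so these are assumptions: normal values with a random subject effect, no drug effect, 2.5% or 5% of values beyond a limit, within-subject correlation 0.5 or 0.8, 400,000 simulated subjects per setting. Percentage with an open-label shift, five open-label draws:

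| Beyond limit | Correlation | Study baseline | Pre-open-label baseline |
|---|---|---|---|
| 2.5% | 0.5 | 7.86 | 7.85 |
| 2.5% | 0.8 | 4.46 | 4.44 |
| 5% | 0.5 | 13.55 | 13.57 |
| 5% | 0.8 | 7.56 | 7.54 |

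- Against the study baseline this is 131 × 0.0446 = 5.8 to 131 × 0.1355 = 17.8 subjects. With four draws the rates are 3.9-11.6%, or 5.1 to 15.2 subjects.
- The share of those shifts already present at Week 24 is about 11-25% over the settings with four or five draws, roughly 1-3 of 131 subjects.
- With five draws, changing the baseline removes about 1.2-2.7 shifts per 131. It adds about as many in subjects who were abnormal on Day 1, normal at Week 24 and abnormal again later. The net change is zero.
- If values close in time are more alike than values far apart, the study baseline gives about 3-9% more shifts in relative terms.

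A cruder range without a model: if 1-10% of 131 placebo subjects develop an ANC grade shift and 25-100% of these persist, the number counted twice runs from 131 × 0.01 × 0.25 = 0.3 to 131 × 0.10 × 1.00 = 13.1.

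**The case against.** The strongest reply is that a value before any investigational product is a valid untreated reference. For placebo subjects, Day 1 and Week 24 are both untreated, so neither is wrong. The SAP follows Protocol 10.5.5, and one baseline keeps the arms comparable. Placebo-randomised subjects keep their own column, their double-blind shifts are tabulated separately, and SAP 10.6 plans no safety testing, so no inference depends on this choice.

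Much of that stands. It is why the study-baseline tables should stay and why the matter is modest. It does not remove the double counting: separate phase tables do not show whether the same subject contributes to both, and the pooled open-label display in Protocol 10.4.4 loses the placebo column.

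A reader might infer several stronger things that the documents or the arithmetic do not support:

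- **That the study baseline generally inflates open-label shift counts.** Under exchangeable values the two baselines give the same rate. Material inflation would need lasting placebo-period change, for which the documents give no data.
- **That 28-46% of these shifts are misplaced.** That is the simulated share beyond the limit at any double-blind draw. Most of those subjects were normal again by Week 24, and a pre-open-label baseline would not reclassify them.
- **That all laboratory tables are affected.** The shift table covers ANC only and the change summaries ANC, ALT and AST. The liver-test abnormality incidence is not defined relative to baseline.
- **That the C-SSRS shift table, "compared to baseline will be provided by treatment group separately for the DBTP and OLTP", needs the same change.** It has its own baseline rule in SAP 6.3, and no calculation here bears on it.

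**Conclusion.** The point holds as one of misattribution and double counting in descriptive tables. SAP 6.3 and 10.6.2 together measure placebo-randomised subjects' open-label ANC shifts and ANC, ALT and AST changes from before 24 drug-free weeks. An abnormality that arose on placebo and is still present in the open-label window is tabulated in both phases.

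The likely size is small: roughly 1-3 of 131 subjects, with little or no net inflation. That rests on assumed abnormality rates and correlations. It also takes all 131 as entering the open-label phase, which is an upper limit because Protocol 7.2.24 admits only those who completed the double-blind phase without ending treatment early. The primary analysis is untouched. This is a worthwhile, inexpensive improvement rather than a serious flaw.

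**What to change.** In SAP 10.6.2, keep the study-baseline tables for all arms. Add, for placebo-randomised subjects only, a separate open-label ANC shift table and an ANC, ALT and AST change summary against a pre-open-label baseline. Define it as the last value before the first open-label dose, including the pre-dose Week 24 sample. This mirrors what SAP 10.1 already does for efficacy.

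Do not swap the baseline in one column of a shared table, because arms with different references would then stand side by side.

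In SAP 6.4, assign a Week 24 sample taken before the first open-label dose to the double-blind phase only, and align the Week 24 and Week 28 visit windows with that rule.

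The cost is a few sentences in the SAP and one extra display that must be clearly labelled. No new samples are needed.

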10.6.3 Vital Signs

The analyses of vital signs (systolic/diastolic blood pressure and weight) will include summary statistics of change from baseline over time by treatment group.

Systolic blood pressure and diastolic blood pressure may be analyzed by change from baseline in categories: 10-20 mmHg and \geq 20 mmHg and analyzed for SBP >140 mmHg (Yes vs. No) and DBP > 90 mmHg (Yes vs. No) at each time point.

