- ⁶ Entry into the open-label treatment phase using the IVR/IWR System must occur only after completion of all double-blind treatment phase procedures and prior to the first dose of open-label AMG 334
- ⁷ Height and weight, measured without shoes. Height to be collected at the initial screening phase visit only.
- ⁸ Systolic/diastolic blood pressure, heart rate and body temperature. Blood pressure to be obtained after the subject has been in a semi-recumbent position (partial semi-Fowler's position) or supine position in a rested and calm state for at least 5 minutes. At least 2 measurements (separated by at least 5 min) should be made and the average recorded. The position selected for a subject should be used for all blood pressure measurements throughout the study.
- ⁹ Pregnancy testing for women of childbearing potential (WOCBP) **Note: Additional on treatment pregnancy testing may be performed at the investigator's discretion or per local laws and regulation.**
- ¹⁰ Samples for PK assessment will be serum.
- ¹¹ PK samples collected at a study visit during which investigational product will be administered should be collected before dosing with investigational product (trough)
- ¹² Only subjects participating in the optional PK substudy (must have provided informed consent for the PK substudy) will have blood samples collected on day 8 and day 64. The PK substudy sampling window is ± 3 consecutive calendar days.
- ¹³ For subjects who provided informed consent for the pharmacogenetic studies, DNA will be obtained from the cell pellet collected in the plasma tube used for the biomarker development sample. Therefore, additional sampling is not required.
- ¹⁴ Clinical Outcomes Assessments (COAs) and Patient-reported Outcomes (PROs) to be collected by subjects using eDiaries. The HIT-6 is to be completed during applicable study visits before invasive procedures (eg, blood draws) and investigational product administration.

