7.2.5 Physical Measurements

The following measurements are to be performed: height (initial screening only) and weight. Height and weight are to be measured without shoes.

All measurements are to be recorded on the Physical Measurements CRF.

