7.2.6 Vital Signs

The following measurements are to be performed: Systolic/diastolic blood pressure, heart rate, and body temperature.

Blood pressure will be measured in the following manner:

- Subjects should be lying in a semi-recumbent position (partial semi-Fowler's position) or supine position quietly and comfortably for at least 5 minutes. The upper arm should be bare without constrictive clothing and supported at heart level.
- Caffeine, exercise, and smoking should be avoided for at least 30 minutes prior to measurement.
- An appropriately-sized cuff (cuff bladder encircling at least 80 percent of the arm) should be used to ensure accuracy. At least two measurements (separated by at least 5 min) should be made and the average recorded. If there is a high value, it is acceptable to wait approximately 30 minutes before the next two blood pressure measurements are taken for the purpose of averaging and recording in the CRF.
- Blood pressure will initially be recorded in both of the subject's arms unless a concomitant condition favors the use of a particular arm. The arm with the higher systolic reading at initial screening should then be used for blood pressure determinations throughout the study.
- Neither the subject nor the observer (measurer) should talk during measurement.

The position selected for a subject (ie, semi-recumbent or supine) should be the same that is used throughout the study and documented on the Vital Signs CRF.

The temperature location selected for a subject should be the same that is used throughout the study and documented on the Vital Signs CRF.

All measurements are to be recorded on the Vital Signs CRF.

If abnormalities in vital signs are found and they are considered to be adverse events, record on the adverse event summary CRF.

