7.2.10 Electrocardiogram (ECG)

The subject must be in a supine position in a rested and calm state for at least 5 minutes before the ECG assessment is conducted. If the subject is unable to be in the supine position, the subject should be in most recumbent position as possible. The ECG must include the following measurements: Heart Rate, QRS, QT, QTc, and PR intervals.

Sites will use ECG equipment supplied by Amgen. The central reader will review all ECGs. Once signed, the original ECG tracing will be retained with the subject's source documents. At the request of Amgen, a copy of the original ECG will be made available to Amgen.

It is the responsibility of the investigator to determine if the ECG tracings are consistent with a subject's safe participation in the study.

Any ECG abnormality noted by the central reader must be evaluated by the investigator and discussed with the Amgen medical monitor as deemed necessary to determine if the ECG finding is representative of an unstable or clinically significant medical condition. Please refer to the central ECG reader manual for details.

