10.1.1.2 Secondary Endpoints

Efficacy:

- Achievement of at least a 50% reduction from baseline in mean monthly migraine days over the last three months (months 4, 5, and 6) of the double-blind treatment phase
- Change from baseline in mean monthly acute migraine-specific medication treatment days over the last three months (months 4, 5, and 6) of the double-blind treatment phase

Safety:

- Adverse events
- Clinical laboratory values and vital signs
- Anti-AMG 334 antibodies

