10.5.5 Safety Endpoints

For safety endpoints, all randomized subjects who received at least one dose of investigational product (ie, safety analysis set) will be analyzed **according to the randomized treatment unless a subject has received the incorrect dose during the entire double-blind treatment phase.**

The Medical Dictionary for Regulatory Activities will be used to code all adverse events.

Subject incidence rates (double-blind treatment phase) and **exposure-adjusted** subject incidence rates (**OLTP**) of all treatment-emergent adverse events will be tabulated by treatment groups and by system organ class and preferred term. Tables of fatal adverse events, serious adverse events, adverse events leading to withdrawal from investigational product, treatment-related adverse events, serious treatment-related adverse events, and adverse events of special interest also will be provided.

In addition, summaries of treatment-emergent adverse events and summaries of serious treatment emergent adverse events will be provided by preferred term in descending order of frequency. The analyses of safety laboratory endpoints will include summary statistics over time by treatment group **for selected analytes**. Shift tables of the worst on-study safety laboratory toxicity based on grade relative to baseline will be tabulated by treatment group.

The analyses of vital signs will include summary statistics over time by treatment group.

The incidence and percentage of subjects who develop anti-AMG 334 antibodies (binding and if positive, neutralizing) at any time will be tabulated by treatment group.

All safety analyses will be performed for the double-blind treatment phase and **OLTP** separately.

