10.7.1 Exposure-Response Analysis

Exposure-Response (E-R) analysis will be performed. Please refer to the E-R SSAP for additional details.

11. Changes from Protocol-specified Analyses

N/A

12. Literature Citations / References

- Fitzmaurice GM, Laird NM and Ware JH. (2004). Applied Longitudinal Analysis. New York: John Wiley and Sons.
- Breslow, N. E. and Clayton, D. G. (1993), Approximate Inference in Generalized Linear Mixed Models, *Journal of the American Statistical Association*, 88, 9–25.
- Wolfinger, R. and O'Connell, M. (1993), Generalized Linear Mixed Models: A Pseudo Likelihood Approach, *Journal of Statistical Computation and Simulation*, 4, 233–243.
- Rubin, D. B. (1987), Multiple Imputation for Nonresponse in Surveys, New York: John Wiley & Sons, Inc.
- Heinze, G. and Schemper, M. (2002), A Solution to the Problem of Separation in Logistic Regression, *Statistics in Medicine*, 2002; 21:2409–2419.
- Quade, D. (1966), Rank analysis of covariance, University of North Carolina, Institute of Statistics Mimeo Series. No. 483
- Fairclough DL1, Cella DF. Functional Assessment of Cancer Therapy (FACT-G): non-response to individual questions. *Qual Life Res*. 1996 Jun;5(3):321-9.

13. Prioritization of Analyses

The tables, listings and figures for Flash Memo of primary analysis at week 24 will be prioritized.

14. Data not Covered by This Plan

There are no plans to specifically analyze or summarize the following data points.

- ECG interval data
- PK
- CCI [REDACTED]
- CCI [REDACTED]

15. Appendices

Appendix A. Technical Detail and Supplemental Information Regarding Statistical Procedures and Programs

A1 Generalized Linear Mixed Model

Generalized mixed effects repeated measure model fits data with correlations or nonconstant variability and where the response is not necessarily normally distributed, which is also known as generalized linear mixed models (GLMM). The correlations can arise from repeated observation of the same sampling units, shared random effects in an experimental design, spatial (temporal) proximity, multivariate observations, and so on.

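### SAP 10.6.3 plans vital-sign summaries for blood pressure and weight only, so heart rate and body temperature, which the protocol counts as vital signs, have no specified summary by treatment group

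*SAP*

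**What the plan says.** **Protocol.** Section 7.2.6 defines the vital signs: "The following measurements are to be performed: Systolic/diastolic blood pressure, heart rate, and body temperature". Footnote 8 to the Schedule of Assessments gives the same list: "Systolic/diastolic blood pressure, heart rate and body temperature". Section 10.1.1.2 includes "Clinical laboratory values and vital signs" among the secondary safety endpoints, and SAP 4.1.2 repeats that line. Section 10.5.5 gives the planned analysis: "The analyses of vital signs will include summary statistics over time by treatment group". Weight is handled separately, under Physical Measurements in 7.2.5: "The following measurements are to be performed: height (initial screening only) and weight".

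**SAP.** Section 10.6.3 reads: "The analyses of vital signs (systolic/diastolic blood pressure and weight) will include summary statistics of change from baseline over time by treatment group". It then allows optional categorical analyses of systolic and diastolic pressure. Section 10.6.5 tabulates the incidence of ECG diagnoses and declines to summarise QTc. Section 14 lists "ECG interval data" among the data with no planned summary. Section 11 (Changes from Protocol-specified Analyses) is answered N/A.

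**The concern.** A programmer working from SAP 10.6.3 would produce tables for blood pressure and weight and stop there. Two measured components of a named safety endpoint would then have no between-group summary, and nothing in the SAP records that the protocol's plan was narrowed.

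Heart rate is the one that matters more. The product blocks the receptor of a peptide that Protocol 2.1 describes as a strong vasodilator, and Protocol 9.3 sends possible cardiovascular and cerebrovascular events to independent adjudication. Heart rate is taken at the same visits as blood pressure, so a placebo-controlled description of its change over 24 weeks is available at almost no cost. What is at stake is the completeness of the descriptive safety report. No hypothesis test or error rate is involved, because SAP 10.6 does no between-group testing of safety data.

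**Working it through.** No arithmetic applies. The check sets the protocol's definition, schedule and planned analysis beside every SAP section that could report the two measures.

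1. **How often they are measured.** Protocol Table 2 marks vital signs at initial screening, week -4, day 1 before randomization, and weeks 4, 8, 12, 16, 20 and 24/ET. Table 3 marks them from week 28 through week 100/ET, at the dose-increase visit, 12 weeks after it, and at safety follow-up. The blank cells are day 1 after randomization and the continuation column for week 24. Each belongs to a visit that already has a mark, so no main-study clinic visit lacks vital signs.

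2. **Item by item.**

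| Measure | Class in protocol | Summary specified in SAP |
|---|---|---|
| Systolic/diastolic blood pressure | Vital sign (7.2.6) | Yes, 10.6.3 |
| Heart rate | Vital sign (7.2.6) | None |
| Body temperature | Vital sign (7.2.6) | None |
| Weight | Physical measurement (7.2.5) | Yes, 10.6.3 |

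Two of three vital signs have no summary if blood pressure counts once, and two of four if systolic and diastolic count separately.

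3. **Whether the protocol allows a selection.** In Protocol 10.5.5 the laboratory sentence is limited to selected analytes. The vital-signs sentence in the same section carries no such limit.

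4. **Whether another SAP section covers them.** Sections 10.6.1 to 10.6.8 deal in turn with adverse events, neutrophil count and liver tests, vital signs, the suicidality scale, ECG, antibodies, exposure and concomitant medication. Outside 10.6.3 the only candidate is the ECG, which does record the rate: "The ECG must include the following measurements: Heart Rate, QRS, QT, QTc, and PR intervals". But 10.6.5 plans only the incidence of diagnoses, so ECG heart rate has no specified summary either.

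5. **Whether document versions explain it.** The SAP was written to Protocol 1.0 (SAP Section 1). The Amendment 2 description of changes lists none to Protocol 7.2.6, so the version gap does not account for the difference.

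**The case against.** **Other safeguards exist.** Protocol 7.2.6 sends vital-sign abnormalities judged to be adverse events to the adverse event form, and 9.2.1 treats those needing treatment as adverse events. SAP 10.6.1 tabulates adverse events by treatment group, 10.6.5 tabulates ECG diagnoses, and an independent committee reviews safety during the double-blind phase. This stands, and it limits the point to the measured values. It does not remove it: Protocol 9.2.1 says that abnormal values without clinical significance are in general not recorded as adverse events, so a small average change would not reach those tables.

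**The general rule in SAP 10.1.** That section promises descriptive statistics at each visit, which could be read to cover everything. It names no vital sign, however, and 10.6.3 is the specific section with its own list.

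**Pharmacology.** The mechanism bears most directly on blood pressure, which is summarised. Protocol 2.2 reports no significant ECG or blood-pressure effect in the monkey cardiovascular study, and the clinical summaries in 2.3 describe no heart-rate signal. This is fair and keeps the severity down. Temperature matters less still.

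**Stronger readings the documents do not support.**
- A reader might infer that SAP Section 14 excludes ECG heart rate as interval data. Protocol 7.2.10 lists heart rate as its own item and 10.6.5 declines only QTc, so the SAP is silent on it. Two entries in Section 14 are blacked out and prove nothing either way.
- A reader might infer that weight was put in to replace heart rate. The text shows only that weight is grouped there.
- A reader might count the readings, at most 459 × 6 = 2,754 after baseline in the double-blind phase at full attendance. That measures available data, not harm.

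**Conclusion.** The point holds as an inconsistency in safety reporting between the protocol and the SAP. Measured heart rate and body temperature, two of the protocol's three vital signs, have no specified summary by treatment group, and the SAP does not declare the departure. The consequence is bounded: marked abnormalities would surface through adverse events or ECG diagnoses, while a modest mean shift against placebo would not be displayed. The primary and secondary efficacy analyses are untouched, and no heart-rate effect is alleged. The conclusion assumes that 10.6.3 is applied as written and that no other planned output, outside the documents available, reports these measures. It should be corrected, but it does not threaten the trial's main conclusions.

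**What to change.** In SAP 10.6.3, name heart rate and body temperature alongside systolic and diastolic blood pressure in the summaries of change from baseline by visit and treatment group, for each study phase. Keep weight as an additional item, labelled as a physical measurement. If the sponsor prefers to leave either measure out, SAP Sections 11 and 14 should say so and give the reason; that would settle the inconsistency but would not supply the missing summary.

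The cost is two more parameters in a table that is already planned, using data already collected.

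One minor tidy-up belongs in the same section. The optional blood-pressure change categories, 10-20 mmHg and ≥ 20 mmHg, both contain a change of exactly 20. Writing the first as ≥ 10 and < 20 mmHg removes the overlap.
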